## INTRODUCTION

Extensor tendon injuries of the hand are common due to the superficial anatomical location of the tendons and the relatively thin soft-tissue envelope over the dorsum of the hand and wrist. Injuries involving zones VI to VIII, as defined by Verdan's classification, are particularly prone to postoperative complications, including peritendinous adhesions, extensor lag, stiffness, and delayed return to function. Despite advances in suture techniques and standardized rehabilitation protocols, adhesion-related functional impairment remains a persistent clinical challenge following extensor tendon repair [1,2].

Postoperative adhesions have been reported in up to 30–40% of extensor tendon injuries, even when repairs are performed under optimal conditions and followed by early controlled mobilization [3]. Adhesion formation results from an exaggerated fibroproliferative response within the peritendinous environment, leading to impaired tendon gliding, loss of excursion, and secondary joint stiffness. This pathological process is particularly problematic in zones VI–VIII, where tendons traverse beneath the extensor retinaculum and are closely related to subcutaneous tissues, increasing susceptibility to friction and scarring [4].

Several strategies have been explored to mitigate adhesion formation after tendon repair, including refinement of core suture techniques, epitendinous augmentation, early active motion protocols, and pharmacologic or mechanical anti-adhesion barriers [5,6]. While early mobilization has improved outcomes compared with prolonged immobilization, it has not eliminated adhesion-related morbidity, and aggressive motion may increase the risk of repair site failure in certain clinical scenarios [7].

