The safety and clinical efficacy of HPTC have been well established across a range of surgical applications. Multiple randomized controlled trials and prospective clinical studies by Narayan and colleagues have demonstrated that HPTC promotes faster healing, improved tissue quality, reduced pain, and favourable scarring outcomes in chronic wounds, pressure ulcers, diabetic foot ulcers, venous leg ulcers, and complex reconstructive settings [15–19]. Importantly, these studies consistently report excellent tolerability and an absence of foreign body reactions, supporting the use of HPTC in sensitive anatomical environments.

Despite this growing body of evidence, the application of HPTC as a biologic wrap around extensor tendon repair sites has not previously been evaluated in a randomized controlled clinical trial. Given the strong biological plausibility of type I collagen scaffolds, the demonstrated benefit of biologic wraps in reducing tendon adhesions, and the reproducible clinical performance of HPTC in other tissue systems, it is logical to investigate whether HPTC wrapping can improve functional outcomes following extensor tendon repair of the hand.

We therefore conducted a multicentric RCT to evaluate the effect of HPTC wrap on total active motion, adhesion-related morbidity, and patient-reported outcomes at eight weeks following extensor tendon repair in zones VI–VIII.

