### **Outcome Measures**

The primary outcome measure was total active motion of the involved digit or digits at eight weeks postoperatively. Total active motion was calculated as the sum of active flexion at the metacarpophalangeal, proximal interphalangeal, and distal interphalangeal joints minus extension deficits. Results were expressed in degrees and as a percentage of the contralateral uninvolved digit or standardized normative values.

Secondary outcomes included QuickDASH scores at six and eight weeks, extensor lag at individual joints measured in degrees at eight weeks, grip strength measured using a calibrated Jamar dynamometer at eight weeks, incidence of adhesion-related events including failure to achieve functional motion thresholds or need for tenolysis, complication rates, time to return to work or activities of daily living, and patient satisfaction scores (Table 1).

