**Table 1: Summary of outcome measures and assessment time points**

Outcome	Assessment time point
Total active motion	8 weeks
QuickDASH	6 and 8 weeks
Extensor lag	8 weeks
Grip strength	8 weeks
Adhesion-related events	Up to 8 weeks
Complications	Intraoperative to 8 weeks
Return to work	Up to 8 weeks
Patient satisfaction	8 weeks

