## **Sample Size Calculation**

The sample size was calculated to detect a clinically meaningful difference in total active motion between the two groups at eight weeks. Assuming a moderate-to-large effect size of 0.75, a two-sided alpha level of 0.05, and a power of 80%, a minimum of 28 patients per group was required. To account for potential attrition and incomplete follow-up, the sample size was increased to 30 patients per group, resulting in a total sample size of 60 participants.

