## **Statistical Analysis Plan**

All analyses were performed using an intention-to-treat approach, including all randomized participants in their allocated groups. A per-protocol analysis will be conducted as a secondary exploratory analysis.

Continuous variables were expressed as mean  $\pm$  standard deviation or median with interquartile range, depending on distribution. Categorical variables will be expressed as frequencies and percentages. Between-group comparisons of the primary outcome were performed using an independent samples t-test for normally distributed data or the Mann–Whitney U test for non-normally distributed data. Proportions of patients achieving good or excellent functional outcomes based on established extensor tendon scoring systems were compared using chi-square or Fisher’s exact tests.

Secondary outcomes were analysed using appropriate parametric or non-parametric tests. Repeated-measures analysis of variance or mixed-effects models was used to evaluate changes in functional scores over time. Effect sizes were reported using Cohen’s d for continuous outcomes and relative risk or odds ratios for categorical outcomes, with corresponding 95% confidence intervals. Two-sided p-values less than 0.05 was considered statistically significant.

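### If complications are uncommon and the control arm has none, the planned ratio gives no useful upper limit on excess harm; a risk difference with a Newcombe interval is a cheap addition

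*Combined protocol and SAP*

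**What the plan says.** The Statistical Analysis Plan section gives two rules that apply to complications. For description: "Categorical variables will be expressed as frequencies and percentages". For the between-arm effect: "relative risk or odds ratios for categorical outcomes, with corresponding 95% confidence intervals". It names no risk difference, no interval for an absolute difference and no rule for zero cells.

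Outcome Measures includes complications among the secondary outcomes ("need for tenolysis, complication rates, time to return to work"). Adhesions are a separate item in the same list: "incidence of adhesion-related events including failure to achieve functional motion thresholds". Table 1 also gives the two their own rows, with complications recorded "Intraoperative to 8 weeks".

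On size, Sample Size Calculation states that "the sample size was increased to 30 patients per group". No complication rate is given anywhere, apart from the adhesion figure in the Introduction: "Postoperative adhesions have been reported in up to 30–40% of extensor tendon injuries".

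**The concern.** A ratio measure divides by the control-arm risk or odds. With 30 patients per arm and a short follow-up, the control arm may have no complications at all. The ratio is then infinite, or undefined if the HPTC arm is also at zero. Its interval cannot tell a reader how large an excess of complications the data still allow.

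That question is worth answering here. The Introduction says that the wrap around extensor tendon repairs "has not previously been evaluated in a randomized controlled clinical trial". Surgical Technique adds two materials in the HPTC arm only: the collagen sleeve and a cyanoacrylate adhesive. The harms at issue are mainly those that the motion outcomes would not show, such as infection or a reaction to the adhesive. With a result such as 0 v 0 or 1 v 0, a report with no usable interval could be read as reassurance that 30 patients per arm cannot give.

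**Working it through.** **Inputs.** 30 per arm (Sample Size Calculation) and 1:1 allocation. The plan's own sample size reproduces: 2 × (1.960 + 0.842)² / 0.75² = 27.9, so 28 per group, raised to 30. The plan states no figure for complications, so their risk p is an assumption, shown as a range.

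**1. How often is the control arm at zero?** The chance is (1 − p)^30.

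| Assumed control risk | Chance of 0/30 |
|---|---|
| 1% | 74% |
| 2% | 55% |
| 3% | 40% |
| 5% | 21% |
| 10% | 4% |
| 15% | 0.8% |
| 30% | 0.002% |

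With 3% risk in both arms, the likeliest splits with a zero control arm (HPTC v control) are:
- 0 v 0: 0.97^60 = 16%
- 1 v 0: 30 × 0.03 × 0.97^59 = 15%
- 2 v 0: 435 × 0.03² × 0.97^58 = 7%

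**2. What does the planned ratio give?**

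*Exact conditional odds ratio.* At 1 v 0 the lower limit ψ solves ψ/(1 + ψ) = 0.025, so ψ = 0.025/0.975 = 0.026. No finite upper limit exists. At 2 v 0 the lower limit solves 435ψ²/(435ψ² + 900ψ + 435) = 0.025, so ψ = 0.19, and the upper limit is again infinite. At 0 v 0 the estimate is 0/0.

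*Relative risk with 0.5 added to each cell.* RR = (a + 0.5)/0.5, where a is the number of HPTC patients with a complication. The standard error of log RR is √[1/(a + 0.5) + 1/0.5 − 2/31].
- 0 v 0: RR 1.0, SE 1.984, interval 0.02 to 49
- 1 v 0: RR 3.0, SE 1.613, interval 0.13 to 71
- 2 v 0: RR 5.0, SE 1.528, interval 0.25 to 100

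These limits are finite, but they depend on the added constant and exclude nothing of interest.

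**3. What does the risk difference give?** The Newcombe interval combines the Wilson limits (l, u) of the two arms, with HPTC as arm 1 and control as arm 2, and d = p₁ − p₂:
- lower = d − √[(p₁ − l₁)² + (u₂ − p₂)²]
- upper = d + √[(u₁ − p₁)² + (p₂ − l₂)²]

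For 0/30, l = 0 and u = z²/(n + z²) = 3.84/33.84 = 0.1135. With zero control events p₂ − l₂ = 0, so the upper limit reduces to u₁. The Wilson limits are 0.0059 to 0.1667 for 1/30 and 0.0185 to 0.2132 for 2/30.

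| HPTC v control | Exact odds-ratio interval | Risk difference, points (95% interval) |
|---|---|---|
| 0 v 0 | estimate undefined; 0 to infinity | 0.0 (−11.4 to 11.4) |
| 1 v 0 | 0.026 to infinity | 3.3 (−8.3 to 16.7) |
| 2 v 0 | 0.19 to infinity | 6.7 (−5.7 to 21.3) |

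With 28 per arm the upper limits become 12.1, 17.7 and 22.6 points.

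**4. Does the same hold when the HPTC arm is the one at zero?** No. At 0 v 3 the exact odds ratio is 0 with an interval of 0 to 2.37, so an upper limit exists.

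**The case against.** The strongest objection is that the trigger is assumed. The documents give no low complication rate. The Introduction's own description of postoperative complications in these zones includes adhesions, extensor lag and stiffness, with adhesions in up to 30–40% of injuries. On that usage a zero control arm is practically impossible (0.002% at 30% risk) and the point does not arise. This objection stands as a condition. Against it, Outcome Measures and Table 1 list adhesion-related events apart from complications, which supports a narrower count.

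A reader might go further than the documents allow in four ways:

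- **That the planned ratio can never have an upper limit.** The plan does not fix an interval method, and a 0.5 correction would give a finite limit. The limit is not useful, but it exists.
- **That any zero arm defeats the plan.** The problem is confined to a zero control arm. With a zero HPTC arm and control events, an exact interval still bounds the ratio from above.
- **That mechanical harm from the wrap goes unmeasured.** Surgical Technique warns against a tight or bulky wrap that hinders gliding. Total active motion, extensor lag and adhesion-related events would pick that up, and the first two are continuous and unaffected by zero cells.
- **That information is lost or a conclusion becomes wrong.** The planned counts fully determine the risk difference, so a reader could work it out. The plan sets no safety margin and announces no safety claim.

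The last of these limits the weight of the point but does not remove it. Naming the measure in advance commits the trial to reporting it and fixes the method before results are seen.

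**Conclusion.** The point holds as a conditional, low-cost improvement. If complications are counted separately from adhesion-related events and are uncommon (roughly 5% or less, where the chance of a zero control arm is 21% or more), there is a material chance that the only planned between-arm measure will give no useful upper limit on excess harm. At 10% the chance is 4%, and at 15% it is under 1%. All these rates are assumptions, because the documents state none.

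The risk difference stays finite in each case, with upper limits of 11.4, 16.7 and 21.3 points at 0, 1 and 2 v 0. These are wide, and they show how little 30 patients per arm can exclude. The primary analysis, the sample size and the other categorical outcomes are not affected.

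**What to change.** In the Statistical Analysis Plan section, for patients with at least one complication:

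- keep the planned counts and percentages, and the ratio where it can be estimated;
- add the between-arm risk difference (HPTC minus control) with a Newcombe 95% confidence interval;
- state that any safety statement will rest on the upper limit of that interval.

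An exact (Clopper-Pearson) interval for each arm's risk is optional; at 0/30 its upper limit is 1 − 0.025^(1/30) = 11.6%. Leave the ratio measures for the other categorical outcomes as planned.

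The cost is about two sentences of text and a few lines of code on counts already collected, with no new data. The downside is that a wide interval makes the safety statement look less favourable.
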